Donepezil, solifenacin

Title of Study:

A phase II, dose titration study of CPC-201 in Patients with Dementia of Alzheimer's Type

Number of clinical centers:

Multicenter

Objectives:

Primary:

• To determine the optimal initial dose and subsequent dose titration schedule (rate and increment) for CPC-201.

Secondary:

• To evaluate the safety and tolerability of CPC-201 as a function of dose and initial rate of dose titration.

Methodology:

This is a Phase II, ascending dose study of CPC-201 in patients with dementia of Alzheimer's type to determine the optimal dose titration schedule. The study involves a step wise cohort design in two different patient populations: Group 1 will consist of patients who have been treated with donepezil 5 or 10 mg/day (given once daily) for at least 4 weeks just prior to Day1. Group 2 will consist of patients who have never been treated with donepezil before (donepezil naïve) or who have not received any other AChEI for the past 6 months.

In this study, donepezil dose will be increased at weekly intervals, in accordance with the schedules given below, to its first intolerable dose (FID) or maximum allowed dose (MAD) of 60mg/day (40 mg/day for Cohort 3c) together with solifenacin 15 mg/day. If a patient does not tolerate a donepezil dose higher than 40mg/day with solifenacin 15 mg/day, the solifenacin dose can be increased to 20mg/day per the Investigator's decision.

	Cohort 1	1 st week: 20mg donepezil + 15mg solifenacin			
		2 nd week: 30mg donepezil + 15mg solifenacin			
		3 rd week: 40mg donepezil + 15mg solifenacin			
		4 th week: 50mg donepezil + 15mg (or 20mg) solifenacin			
		5 th week: 60mg donepezil + 15mg (or 20mg) solifenacin			
	Cohort 2*	1 st week: 20mg donepezil + 15mg solifenacin			
		2 nd week: 40mg donepezil + 15mg solifenacin			
		3 rd week: 60mg donepezil + 15mg (or 20mg) solifenacin			
	Cohort 3*	1 st week: 20mg donepezil + 15mg solifenacin			
		2 nd week: 60mg donepezil + 15mg (or 20mg) solifenacin			
*	*: The dose titration schedule of Cohorts 2 and 3 may be altered based on Cohort 1 result.				
Р	Per this amendment, patients currently treated with donepezil (Group 1) will receive solifenacin 15				

mg/day during a two week run in period; donepezil treatment will continue at 10mg/day. Once on 15 mg/day of solifenacin for two weeks (based upon the investigator judgment), the donepezil dose will be increased at weekly or bi-weekly intervals, in accordance with the schedules given below, to its first intolerable dose (FID) or maximum allowed dose (MAD) of 60mg/day.

Cohort 1b	1 st -2 nd week: 10mg donepezil + 15mg solifenacin				
	3 rd week: 20mg donepezil + 15mg solifenacin				
	4 th week: 30mg donepezil + 15mg solifenacin				
	5 th week: 40mg donepezil + 15mg solifenacin				
	6 th week: 50mg donepezil + 15mg (or 20mg) solifenacin				
	7 th week: 60mg donepezil + 15mg (or 20mg) solifenacin				
Cohort 2b	$1^{st} - 2^{nd}$ week: 10mg donepezil + 15mg solifenacin				
	3 rd week: 20mg donepezil + 15mg solifenacin				
	4 th week: 40mg donepezil + 15mg solifenacin				
	5th week: 60mg donepezil + 15mg (or 20mg) solifenacin				
Cohort 3b	$1^{st} - 2^{nd}$ week: 10mg donepezil + 15mg solifenacin				
	3 rd week: 20mg donepezil + 15mg solifenacin				
	4 th week: 60mg donepezil + 15mg (or 20mg) solifenacin				

*: The dose titration schedule of Cohorts 2 and 3 may be altered based on Cohort 1 result.

Per this amendment, all patients not treated with an AchEI for at least 6 months (Group 2) will receive 15mg solifenacin and 10mg donepezil for 2 weeks before starting donepezil titration.

Each cohort will include approximately 6 patients donepezil-treated (Group 1) and approximately 6 patients not treated with an AchEI for at least 6 months (Group 2). Within each cohort, Group 2 patients will be enrolled only when at least 3 Group 1 patients have completed dose titration per protocol.

Patients will be enrolled in Cohort 2 only when patients enrolled in Cohort 1 have safely completed titration. Similary, patients will be enrolled in Cohort 3 only when patients enrolled in Cohort 2 have safely completed titration.

Cohorts 1 and 2 were completed prior to this amendment. This amendment is to change the dosing regimen of cohort 3. All subjects entering the study in cohort 3c will start with a dose regimen of 10mg donepezil + 15mg solifenacin and will continue to increase the donepezil dose by 5mg increments every 7 days (or up to 14 days per PI discretion) up to 40mg or the MTD.

Cohort 3c	1 st week: 10mg donepezil + 15mg solifenacin
	2 nd week: 15mg donepezil + 15mg solifenacin
	3 rd week: 20mg donepezil + 15mg solifenacin
	4 th week: 25mg donepezil + 15mg solifenacin
	5 th week: 30mg donepezil + 15mg solifenacin
	6 th week: 35mg donepezil + 15mg solifenacin
	7 th week: 40mg donepezil + 15mg solifenacin

Patients reaching their FID or having completed one week treatment with donepezil 40mg/day, have two options.

Option 1: Patient will be allowed to immediately enter a long term extension at their maximum tolerated

dose (MTD) or MAD.

Option 2: Patients may choose not to enter the long term extension, in which case the Investigator will decide whether the patient should discontinue high dose of donepezil without down-titration, or whether donepezil should be downtitrated to their own standard of donepezil dose. Whatever the decision, the patient will be treated at least an additional 7 days with solifenacin 15 mg/day.

Number of patients planned:

To ensure a suitable number of subjects to evaluate the optimal dose titration schedule, approximately 6 patients per population group per cohort will be enrolled.

Diagnosis and main criteria for inclusion:

Males and females suffering from AD

Inclusion Criteria:

- Signed an Institutional Review Board (IRB) approved informed consent document indicating that they understand the purpose of and procedures required by the study and are willing to participate in the study and comply with all study procedures and restrictions. Informed consent must be obtained from the patient and/or a designated representative prior to initiating screening procedures to evaluate eligibility for the study.
- 2) Aged 50 89 years inclusive.
- 3) Meeting the diagnosis of probable AD consistent with:
 - Revised National Institute on Aging-Alzheimer's Disease Association (NIA-ADA) criteria and
 - Diagnostic and Statistical Manual of Mental Disorders (DSM IV) criteria.
- 4) Mild to severe severity (Mini-Mental Status Exam [MMSE] scores 7 24 inclusive).
- 5) Rosen-Modified Hachinski Ischemia Score of ≤4.
- 6) Have a suitable caregiver to supervise the at-home administration of study drugs and observe for AEs.
- 7) Patients will be required to have been treated with donepezil 5 or 10 mg/day (given once daily) for at least 4 weeks just prior to Day1 for Population (group) 1 or;

Patients have never been treated with donepezil before (donepezil naïve) or who have not received any other AChEI for the past 6 months for Population (group) 2.

8) Patients must be in generally good health as indicated by their medical history and physical examination, vital signs, electrocardiogram (ECG), and standard laboratory tests.

Key exclusion criteria:

The criteria for exclusion of a subject from enrollment in the study are as follows:

- 1) Women of child bearing potential.
- 2) History or presence of a seizure disorder.
- 3) Current unstable peptic ulcer disease, urinary or gastric retention; asthma or obstructive pulmonary disease.
- 4) History or presence of bladder outflow obstruction, gastrointestinal obstructive disorder or reduced GI motility, or narrow-angle glaucoma.
- 5) History or presence of gastrointestinal, hepatic, or renal disease, or other condition known to interfere with the absorption, distribution, metabolism or excretion of drugs.
- 6) Renal and hepatic dysfunction with:
 - Total Bilirubin: >1.5 x UNL

- AST: >2.5 x UNL
- ALT: >2.5 x UNL
- Serum Creatinine: >1.5 x UNL
- Creatinine Clearance: <30 mL/min (calculated by Cockcroft and Gault equation)
- 7) History or presence of myasthenia.
- 8) History or family history of Prolonged QT Syndrome.
- 9) History of unexplained syncope or family history of unexplained syncope or sudden death.
- 10) Myocardial infarction or hospitalization for congestive heart failure within 6 months.
- 11) ECG findings of:
 - Complete Left Bundle Branch Block;
 - Ventricular pacing;
 - 2nd degree or 3rd degree AV block;
 - Atrial fibrillation or atrial flutter;
 - HR <45 or >100;
 - PR >220 msec; or
 - QTcF >450 msec in male, >470 msec in female
- 12) Known hypersensitivity to donepezil, solifenacin or related drugs.
- 13) History of drug significant allergy.
- 14) History of substance abuse, known drug addiction, or positive test for drugs of abuse or alcohol.
- 15) Patients treated with the following medications within 8 weeks of screening
 - Peripherally acting anticholinergics (such as drugs for the treatment of overactive bladder disorder),
 - Psychoactive medications (including antipsychotics, antidepressants, anxiolytics or sedative hypnotics) having significant anticholinergic effects and/or believed to affect cognitive function.

Other medications are acceptable, at the investigators discretion, if dosage is held stable for at least 4 weeks prior to screening and throughout the study.

- 16) Patients considered unlikely to co-operate in the study, and/or poor compliance anticipated by the investigator.
- 17) Patients hospitalized within 4 weeks of screening.
- 18) Any other clinically relevant acute or chronic diseases which could interfere with patients' safety during the trial, or expose them to undue risk, or which could interfere with study objectives.
- 19) Patients who have participated in another clinical trial with an investigational drug within previous 30 days.

Investigational product (IP)

Donepezil (Aricept[®] or generic equivalent): 5 mg, 10 mg tablet Solifenacin (Vesicare[®]): 5 mg, 10 mg tablets Placebo (Similar in size to donepezil 10 mg or solifenacin 5 mg/10 mg tablets

	l				
					1
					Ī
					•

Duration of treatment:

Screening: 4 weeks

Dosing: up to 7 weeks

Reference therapy, dosage and mode of administration:

None

Statistical Analysis:

Since the objective of this study is to determine the optimal initial dose and subsequent dose titration schedule, the data will be analyzed only by means of descriptive statistics to reveal possible trends that will help guide the design of future, more definitive, clinical trials.

Sample size calculations:

No formal sample size calculation has been made. Based on experience from previous similar studies, a total 4-6 evaluable subjects per group per cohort is considered sufficient.

Version date: 07/22/2016

Page 14 of 53

Version date: 07/22/2016

Page 15 of 53

Version date: 07/22/2016

Page 16 of 53

Version date: 07/22/2016

Page 17 of 53

Version date: 07/22/2016

Page 18 of 53

Version date: 07/22/2016

Page 19 of 53

Version date: 07/22/2016

Page 20 of 53

2 OBJECTIVES

2.1 Primary objective

To determine the optimal initial dose and subsequent dose titration schedule (rate and increment) for CPC-201.

2.2 Secondary objective

To evaluate the safety and tolerability of CPC-201 as a function of dose and initial rate of dose titration.

3 INVESTIGATIONAL PLAN

3.1 Overall Study design

This is a Phase II, ascending dose study of CPC-201 in patients with dementia of Alzheimer's type to determine the optimal dose titration schedule. The study involves a step wise cohort design in two different patient populations: Group 1 will consist of patients who have been treated with donepezil 5 or 10 mg/day (given once daily) for at least 4 weeks just prior to Day1. Group 2 will consist of patients who have never been treated with donepezil before (donepezil naïve) or who have not received any other AChEI for the past 6 months.

In this study, donepezil dose will be increased at weekly intervals, in accordance with the schedules given below, to its first intolerable dose (FID) or maximum allowed dose (MAD) 60 mg/day (40 mg/day for Cohort 3c) together with solifenacin 15 mg/day. If a patient does not tolerate a donepezil dose higher than 40mg/day with solifenacin 15 mg/day, the solifenacin dose can be increased to 20mg/day per the Investigator's decision.

Cohort 1	1 st week: 20mg donepezil + 15mg solifenacin				
	2 nd week: 30mg donepezil + 15mg solifenacin				
	3 rd week: 40mg donepezil + 15mg solifenacin				
	4 th week: 50mg donepezil + 15mg (or 20mg) solifenacin				
	5 th week: 60mg donepezil + 15mg (or 20mg) solifenacin				
Cohort 2*	1 st week: 20mg donepezil + 15mg solifenacin				
	2 nd week: 40mg donepezil + 15mg solifenacin				
	3 rd week: 60mg donepezil + 15mg (or 20mg) solifenacin				
Cohort 3*	1 st week: 20mg donepezil + 15mg solifenacin				
	2 nd week: 60mg donepezil + 15mg (or 20mg) solifenacin				

*: The dose titration schedule of Cohort 2 and 3 may be altered based on Cohort 1 result.

Per this amendment, patients currently treated with donepezil (Group 1) will receive solifenacin 15 mg/day during a two week run in period; donepezil treatment will continue at 10mg/day. Once on 15 mg/day of solifenacin for two weeks (based upon the investigator judgment), the donepezil dose will be increased at weekly or bi-weekly

intervals, in accordance with the schedules given below, to its first intolerable dose (FID) or maximum allowed dose (MAD) of 60mg/day

Cohort 1b	1 st -2 nd week: 10mg donepezil + 15mg solifenacin					
	3 rd week: 20mg donepezil + 15mg solifenacin					
	4 th week: 30mg donepezil + 15mg solifenacin					
	5 th week: 40mg donepezil + 15mg solifenacin					
	6 th week: 50mg donepezil + 15mg (or 20mg) solifenacin					
	7 th week: 60mg donepezil + 15mg (or 20mg) solifenacin					
Cohort 2b	$1^{st} - 2^{nd}$ week: 10mg donepezil + 15mg solifenacin					
	3 rd week: 20mg donepezil + 15mg solifenacin					
	4 th week: 40mg donepezil + 15mg solifenacin					
	5th week: 60mg donepezil + 15mg (or 20mg) solifenacin					
Cohort 3b	$1^{st} - 2^{nd}$ week: 10mg donepezil + 15mg solifenacin					
	3 rd week: 20mg donepezil + 15mg solifenacin					
	4 th week: 60mg donepezil + 15mg (or 20mg) solifenacin					

*: The dose titration schedule of Cohorts 2 and 3 may be altered based on Cohort 1 result.

Per this amendment, all patients not treated with an AchEI for at least 6 months (Group 2) will receive 15mg solifenacin for 2 weeks before starting donepezil.

Each cohort will include approximately 6 patients donepezil-treated (Group 1) and approximately 6 patients not treated with an AchEI for at least 6 months (Group 2). Within each cohort, Group 2 patients will be enrolled only when at least 3 Group 1 patients have completed dose titration per protocol.

Patients will be enrolled in Cohort 2 only when patients enrolled in Cohort 1 have safely completed titration. Similary, patients will be enrolled in Cohort 3, only when patients enrolled in Cohort 2 have safely completed titration.

Cohorts 1 and 2 were completed prior to this amendment. This amendment is to change the dosing regimen of cohort 3. All subjects entering the study in cohort 3 will start with a dose regimen of 10mg donepezil + 15mg solifenacin and will continue to increase the donepezil dose by 5mg increments every 7 days (or up to 14 days per PI discretion) up to 40mg or the MTD.

Cohort 3c	1 st week: 10mg donepezil + 15mg solifenacin
	2 nd week: 15mg donepezil + 15mg solifenacin
	3 rd week: 20mg donepezil + 15mg solifenacin
	4 th week: 25mg donepezil + 15mg solifenacin
	5 th week: 30mg donepezil + 15mg solifenacin
	6 th week: 35mg donepezil + 15mg solifenacin
	7 th week: 40mg donepezil + 15mg solifenacin

Patients reaching their FID or having completed one week treatment with donepezil 60mg/day (40 mg/day for Cohort 3c), have two options.

- Option 1: Patient will be allowed to immediately enter a long term extension at their maximum tolerated dose (MTD) or MAD.
- Option 2: Patients may choose not to enter the long term extension, in which case the Investigator will decide whether the patient should discontinue high dose of donepezil without down-titration, or whether donepezil should be downtitrated to their own standard of donepezil dose. Whatever the decision, the patient will be treated at least an additional 7 days with solifenacin 15 mg/day.

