2. PROTOCOL DESIGN

2.1 Design Overview

This is a Phase II, ascending dose study of CPC-201 in patients with dementia of Alzheimer's type to determine the optimal dose titration schedule. The study involves a step wise cohort design in two different patient populations: Group 1 will consist of patients who have been treated with donepezil 5 or 10 mg/day (given once daily) for at least 4 weeks just prior to Day1. Group 2 will consist of patients who have never been treated with donepezil before (donepezil naïve) or who have not received any other

AChEI for the past 6 months.

Original Plan

Donepezil dose will be increased at weekly intervals, in accordance with the schedules given below, to its first intolerable dose (FID) or maximum allowed dose (MAD) 60 mg/day together with solifenacin 15 mg/day. If a patient does not tolerate a donepezil dose higher than 40mg/day with solifenacin 15 mg/day, the solifenacin dose can be increased to 20mg/day per the Investigator's decision.

Cohort 1	1 st week: 20mg donepezil + 15mg solifenacin 2 nd week: 30mg donepezil + 15mg solifenacin 3 rd week: 40mg donepezil + 15mg solifenacin 4 th week: 50mg donepezil + 15mg (or 20mg) solifenacin 5 th week: 60mg donepezil + 15mg (or 20mg) solifenacin
Cohort 2*	1 st week: 20mg donepezil + 15mg solifenacin 2 nd week: 40mg donepezil + 15mg solifenacin 3 rd week: 60mg donepezil + 15mg (or 20mg) solifenacin
Cohort 3*	1 st week: 20mg donepezil + 15mg solifenacin 2 nd week: 60mg donepezil + 15mg (or 20mg) solifenacin

*: The dose titration schedule of Cohort 2 and 3 may be altered based on Cohort 1 result.

Patients reaching their FID or having completed one week treatment with MAD, have two options.

Option 1: Patient will be allowed to immediately enter a long term extension at their maximum tolerated dose (MTD) or MAD.

Option 2: Patients may choose not to enter the long term extension, in which case the Investigator will decide whether the patient should discontinue high dose of donepezil without down-titration, or whether donepezil should be dwn-titrated to their own standard of donepezil dose. Whatever the decision, the patient will be treated at least an additional 7 days with solifenacin 15 mg/day.

First Amendment

After 8 subjects in Cohort 1 and 1 subject in Cohort 2 were enrolled, the protocol was amended to add Cohort 1b and to limit to enroll only Group 1.

Patients currently treated with donepezil (Group 1) will receive solifenacin 15 mg/day

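### The Protocol Summary and Section 3.1 contradict each other on whether Group 2 patients receive donepezil during their 2-week lead-in, and Section 3.1 also conflicts with the Cohort 3c start.

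*Protocol*

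**What the plan says.** All protocol references are to the version dated 07/22/2016.

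- **Protocol Summary, Methodology.** All Group 2 patients "will receive 15mg solifenacin and 10mg donepezil for 2 weeks before starting donepezil titration".
- **Protocol Section 3.1.** A sentence with the same opening, in the same position after the Cohort 1b to 3b tables, says that Group 2 patients "will receive 15mg solifenacin for 2 weeks before starting donepezil". It does not give the donepezil dose that follows.
- **Protocol Section 3.1, Cohort 3c text.** "All subjects entering the study in cohort 3 will start with a dose regimen of 10mg donepezil + 15mg solifenacin". Donepezil then rises in 5 mg steps to 40 mg, each step lasting 7 days or up to 14 at the investigator's discretion. The Summary has the same rule under the label 3c.
- **Protocol Section 3.1, status.** "Cohorts 1 and 2 were completed prior to this amendment", which leaves Cohort 3, now 3c, to be dosed.
- **Protocol Summary, Duration of treatment.** Dosing lasts up to 7 weeks.
- **Enrolment.** The protocol plans about 6 Group 2 patients in each cohort. SAP Section 2.1 says the first amendment added Cohort 1b and was also "to limit to enroll only Group 1".
- **Analysis.** SAP Section 8.2 lists time to FID for each patient without stating when the clock starts.

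**The concern.** A patient cannot take donepezil 10 mg for two weeks and also not yet have started it. Both sentences cover all of Group 2, name no cohort, and present themselves as part of the current amendment. The same mismatch stands in the version dated 01/04/2016, so it survived a further amendment.

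The primary objective is the optimal initial dose and titration schedule, and the secondary objective looks at safety by initial rate of titration. The lead-in is therefore part of what is being studied. If Group 2 patients received different lead-ins under one cohort label, the same elapsed time since first study drug would mean different donepezil exposure. SAP Section 8.3.1.1 counts adverse events from the first dose of study drug and summarises them by cohort. With 4 to 6 evaluable patients per group per cohort, a few patients on a different start could change the description. These are also the patients with the least recent exposure to this drug class.

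**Working it through.** There is no power or sample-size figure to reproduce. The figure that can be checked is the 7-week dosing period.

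**Step 1: the 7-week period.** Cohort 1b: 2 weeks at 10 mg plus 5 weekly steps = 7 weeks. Cohort 3c: 7 doses × 1 week = 7 weeks. Both match the stated maximum with no separate lead-in.

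**Step 2: each text laid over the Cohort 3c schedule** (donepezil 10, 15, 20, 25, 30, 35, 40 mg/day, 7-day steps). Section 3.1 does not say whether its lead-in comes before the schedule or takes the place of weeks 1 and 2, so both are shown. The replacement reading (A2) is an assumption.

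| Reading | Donepezil by week (mg/day) | Day 1 | First donepezil dose | Total weeks |
|---|---|---|---|---|
| A1: solifenacin alone for 2 weeks, then 3c | 0, 0, 10, 15, 20, 25, 30, 35, 40 | 0 | 10 | 9 |
| A2: solifenacin alone in place of weeks 1–2 | 0, 0, 20, 25, 30, 35, 40 | 0 | 20 | 7 |
| B: Summary text, then titration | 10, 10, 15, 20, 25, 30, 35, 40 | 10 | 10 | 8 |
| C: 3c as listed | 10, 15, 20, 25, 30, 35, 40 | 10 | 10 | 7 |

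**Step 3: cumulative donepezil through week 3** = 7 × (sum of the first three weekly doses).

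- A1: 7 × (0 + 0 + 10) = 70 mg
- A2: 7 × (0 + 0 + 20) = 140 mg
- B: 7 × (10 + 10 + 15) = 245 mg
- C: 7 × (10 + 15 + 20) = 315 mg

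**Step 4: fit with the dosing period.** With 7-day steps only A2 and C fit within 7 weeks. The permitted 14-day steps would by themselves take 3c to 7 × 2 = 14 weeks, or 16 with a 2-week lead-in in front. The 7-week figure is thus not reconciled with the step rule either.

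**Step 5: which texts can coexist.** B and C can: two weeks at 10 mg lies within the 7-to-14-day step. Section 3.1's solifenacin-alone sentence agrees with neither, because both have donepezil on day 1.

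**Step 6: time to FID.** Under A1 or A2, counting from first study drug instead of first study donepezil adds 2 × 7 = 14 days. Under B and C the two origins coincide.

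**The case against.** The two sentences look carried over from the 01/04/2016 version, where they followed the Cohort 1b to 3b tables. On that view the Cohort 3c rule governs everyone still to be dosed. SAP Section 2.1 supports it: it gives one 3c start for all subjects and no Group 2 lead-in. This is plausible, but the protocol does not say so. Both sentences remain in force for all of Group 2.

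A reader might infer that the Group 2 lead-in is stated in three ways, or that the initial donepezil dose under study is not fixed. The documents support neither. The 3c schedule is a cohort-wide rule, not a third lead-in statement, and it can accommodate the Summary text. Every current-amendment passage that names a donepezil start for Group 2 or Cohort 3c gives 10 mg. A first dose of 20 mg arises only under the assumed reading A2.

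The harm to the analysis is limited. The study is descriptive, without hypothesis tests. The baseline and adverse-event rules are worded the same under any lead-in, and time to FID is only a patient listing. Protocol Section 9.6 and SAP Section 8.1.4 already provide for dosing data. It also cannot be shown that sites acted on different sections: the assessment schedules, visit procedures and tablet table are not visible in the public documents and may settle the start. These points reduce the size of the concern. They do not remove the contradiction.

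**Conclusion.** The point holds as an internal contradiction with a narrow reach. What is open is whether donepezil is given during the Group 2 lead-in and how long that lead-in lasts. For a Group 2 patient in Cohort 3c this means 0 or 10 mg on day 1. With 7-day steps it means 70 to 315 mg through week 3 and 7 to 9 weeks of dosing; the 140 mg case within that range rests on the assumption that the lead-in replaces weeks 1 and 2.

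About 6 planned patients are affected at most. If the SAP's Group 1 restriction extends to Cohort 3c, none are. The documents do not settle this: the SAP sentence may refer only to Cohort 1b, and the protocol still plans Group 2. Because the trial exists to study the initial dose and schedule, contradictory starting instructions are more than a clerical matter. This review takes no view on which start is right.

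**What to change.** 1. **Protocol.** Reconcile the Summary (Methodology and Duration of treatment) with Section 3.1 so that there is one Group 2 start, consistent with the Cohort 3c schedule and the dosing period. If the lead-in sentences no longer apply to Cohort 3c, say so. The choice is the sponsor's.
2. **Protocol and SAP.** State whether Group 2 is enrolled in Cohort 3c, so that the two documents agree.
3. **SAP.** List the lead-in that each Group 2 patient actually received, and state the origin for time to FID, for example first study drug or first study donepezil dose. The first dose above the lead-in would not serve: a patient who reaches FID at 10 mg would have no start date.

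The cost is a protocol clarification and a sentence or two in the SAP, using dosing data already due to be collected. No change in sample size is needed.

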8.3.1.1 Adverse Events

Adverse events will be classified by system organ class (SOC) and preferred term (PT) according to the most recent version of MedDRA dictionary.

TEAE are defined as events with an onset on or after administration of the first dose of study drug. TEAEs will be summarized, System Organ Class, and preferred term. The following TEAE summaries will be provided:

- Top line summary table including
 - all treatment emergent Adverse Events (TEAEs), treatment related TEAE and treatment unrelated TEAE,
 - Serious treatment emergent Adverse Events (STEAEs), treatment related STEAE and treatment unrelated STEAE
 - Deaths
- Overall (*i.e.*, regardless of severity or relationship to treatment)
- By cohort (*i.e.*, 1, 2, 1b, 3c)
- By study phase (*i.e.*, titration and long term extension)
- By severity grade (mild, moderate, severe)
- By relationship to study drug (definitely, probably, possibly, not related)

Unless otherwise specified, at each level of subject summarization, a subject will be counted only once. If there is more than one occurrence of an event, the event of the worst severity or the worst-case relationship category will be summarized.

Serious Adverse Events (SAEs) will also be summarized by relationship.

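### Carried-over dosing text in the July 2016 protocol conflicts with the Cohort 3c schedule on the opening two weeks and on the maximum dose

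*Protocol*

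**What the plan says.** The July 2016 protocol describes dosing twice, in the Protocol Summary (Methodology) and in Section 3.1. Both contain two blocks that present themselves as the present amendment.

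- **Lead-in block.** For Group 1 it reads "Per this amendment, patients currently treated with donepezil (Group 1) will receive solifenacin 15 mg/day during a two week run in period". It keeps donepezil at 10 mg/day during those two weeks and then escalates to a maximum allowed dose (MAD) of 60 mg/day. It names no cohorts; the tables straight after it are 1b, 2b and 3b. A companion sentence covers all Group 2 patients. In the Protocol Summary it gives solifenacin 15 mg plus donepezil 10 mg for two weeks before titration. In Section 3.1 it gives solifenacin alone for two weeks before donepezil.
- **Cohort 3c block.** It says that Cohorts 1 and 2 are complete and that the amendment changes Cohort 3's regimen. Section 3.1 continues "All subjects entering the study in cohort 3 will start with a dose regimen of"; the Protocol Summary has "All subjects entering the study in cohort 3c will start with a dose regimen of". Both then give the same start (10 mg donepezil with 15 mg solifenacin) and the same table: 15 mg in week 2, ending at "7 th week: 40mg donepezil + 15mg solifenacin".

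The older Cohort 3 table ("2 nd week: 60mg donepezil + 15mg (or 20mg) solifenacin") and Cohort 3b table ("4 th week: 60mg donepezil + 15mg (or 20mg) solifenacin") remain in both places, not marked as closed.

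SAP Section 2.1 assigns the run-in to the first amendment with Cohort 1b, and 3c to the second. SAP Section 8.3.1.1 summarises adverse events for cohorts 1, 2, 1b and 3c.

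**The concern.** A 3c entrant cannot follow both blocks at the default step length. One holds Group 1 at 10 mg through week 2; the other moves every entrant to 15 mg at the start of week 2. For Group 2 the lead-in sentence conflicts with the 3c table and also differs between the Protocol Summary and Section 3.1.

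Initial dose, rate and increment are the primary objective, and each patient's first intolerable dose (FID) and maximum tolerated dose (MTD) are the primary outcome (SAP Section 2.4.1). Cohorts are planned at about 6 patients per group, with 4 to 6 evaluable considered enough. One patient titrated under a different reading is therefore 1/6 = 17% to 1/4 = 25% of a cell, and the label 3c would no longer identify a single schedule. SAP Section 8.2 also lists time to reach the FID, which depends directly on the length of the lead-in.

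**Working it through.** There is no planned calculation to reproduce ("No formal sample size calculation has been made"). The check sets the texts side by side and sums the stated doses.

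**Inputs.** The 3c weekly doses are 10, 15, 20, 25, 30, 35 and 40 mg (Protocol Summary and Section 3.1). Lead-in doses are as described above. Steps are 7 days, with up to 14 days allowed in 3c at the investigator's discretion. Cumulative donepezil = 7 × the sum of the daily doses, one term per week.

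**1. Is 3c consistent with itself?** (40 − 10)/5 + 1 = 7 dose levels, which matches the seven weeks in the table. Yes.

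**2. Donepezil in the first two weeks of a 3c entrant, by governing text:**

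| Group | Text | Week 1 | Week 2 | Total |
|---|---|---|---|---|
| 1 | Run-in block | 10 mg | 10 mg | 7 × (10 + 10) = 140 mg |
| 1 | 3c table | 10 mg | 15 mg | 7 × (10 + 15) = 175 mg |
| 2 | Section 3.1 sentence | none | none | 0 mg |
| 2 | Protocol Summary sentence | 10 mg | 10 mg | 140 mg |
| 2 | 3c table | 10 mg | 15 mg | 175 mg |

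For Group 1 the gap is 35 mg, or 35/140 = 25%. For Group 2 the start of donepezil itself differs: day 1, or after two weeks.

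**3. Effect on later weeks.** The text does not say how a run-in would join the 3c table, so two assumptions are shown. If 5 mg steps follow the run-in, weeks 3 to 8 are 15, 20, 25, 30, 35 and 40 mg, and 40 mg begins in week 8 instead of week 7. If the patient joins the table at week 3, the dose goes from 10 to 20 mg, a 10 mg increment instead of 5 mg. Either the rate or the increment changes.

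**4. The 14-day allowance.** If the investigator extends the first 3c step to 14 days, the two-week total is 14 × 10 = 140 mg, the same as the run-in. So the Group 1 conflict is about the default. It also means that a dosing record of 14 days at 10 mg does not show which text the site was following.

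**5. Maximum dose.** The run-in block gives 60 mg/day with no exception. Against it, the general dosing paragraph in both places gives 40 mg/day for 3c, the 3c regimen sentence stops at 40 mg, and the Section 3.1 exit rule repeats 40 mg/day for 3c.

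**6. Leftover tables.** Cohort 3 is 20, 60 mg and Cohort 3b is 10, 10, 20, 60 mg. Only Cohorts 1 and 2 are declared complete; 3 and 3b carry no status.

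**The case against.** The strongest reply is that the lead-in block is plainly old text. It stands in the version dated 01/04/2016 in the same wording, it escalates according to the schedules that follow it, and the tables directly after it are 1b, 2b and 3b. The SAP attributes it to the first amendment and Cohort 1b. On that reading it never reaches 3c. This is plausible and may well be what was meant. But the current protocol does not say so: the block still presents itself as the present amendment, covers Group 1 without naming cohorts, and 3c is also among the schedules below it. The SAP, whose file name is dated August 2017, could not guide a site at enrolment.

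Two further points stand in part. The SAP says that the first amendment limited enrolment to Group 1, so the Group 2 conflict bites only if Group 2 patients entered 3c; the July protocol still plans about 6 per cohort. And the visit schedules and procedures are not visible in the public copy, so they might settle the week 2 dose.

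A reader might also infer that a new entrant's dose is open among 3, 3b and 3c, that the one-letter label difference is a dispute about scope, or that 3c patients could be taken to 60 mg. The documents do not support this. Both places say that the amendment changes Cohort 3's regimen and attach the same 3c table, and the 40 mg/day limit for 3c is explicit. The SAP describes no enrolment in 3 or 3b, so a patient without an analysis cohort is hypothetical. Contrasts such as 60 against 15 mg in week 2 compare 3c with a schedule it replaced.

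**Conclusion.** The point holds for the lead-in. 3c is the intended replacement for Cohort 3, but operative text from the earlier amendment was left in force-like wording that contradicts it. The size is 10 or 15 mg in week 2 for Group 1 (140 or 175 mg over two weeks), and 0, 140 or 175 mg for Group 2. The MAD conflict is weaker, because one unscoped 60 mg statement stands against several explicit 40 mg statements. The unmarked 3 and 3b tables and the mixed cohort label are supporting labelling defects.

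This rests on 7-day steps, on the public text alone, and, for Group 2, on such patients being eligible for 3c. The documents do not show that any patient was dosed under the wrong text. It should be corrected because it concerns the quantity the trial sets out to determine.

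**What to change.** Reconcile the passages so that the Protocol Summary and Section 3.1 say the same thing:

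- Label each block that refers to the present amendment with its version and the cohorts it governs.
- State whether the Group 1 run-in, the Group 2 lead-in and the 60 mg MAD apply to Cohort 3c, and if a lead-in does apply, how it joins the 3c table.
- Mark the Cohort 3 and 3b tables as superseded or active, and use one label for the new cohort.
- In the SAP, analyse each subject under the schedule actually assigned, and list each 3c subject's days at the starting dose with the reason for any step longer than 7 days.

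Which regimen applies is the sponsor's decision. The cost is wording in two places, the ethics board approval that Protocol Section 12.8 requires for any amendment, a site letter and one extra listing. No additional patients or procedures are needed.
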